# 11. REGULATORY CONSIDERATIONS

### 11.1 Institutional Review of Protocol

This study will be conducted under IND 147595 for infigratinib (pre-assigned). Infigratinib was approved by FDA as Truseltiq pursuant the Accelerated Approval regulations on 28 May 2021 for the indication of previously-treated, unresectable, locally-advanced or metastatic cholangiocarcinoma with a fibroblast growth factor receptor 2 (FGFR2) fusion or other rearrangement, in adults

The protocol, the proposed informed consent and all forms of subject information related to the study (eg, advertisements used to recruit subjects) will be reviewed and approved by the Stanford IRB and Stanford Cancer Institute Scientific Review Committee (SRC). Any changes made to the protocol will be submitted as a modification and will be approved by the IRB prior to implementation. The Protocol Director will disseminate the protocol amendment information to all participating investigators.

### 11.2 Data Sharing with Collaborators

Distributor QED Therapeutics expects to share data from this study with the Helsinn Group (collaborator/partner).

### 11.3 Data and Safety Monitoring Plan

The Stanford Cancer Institute Data and Safety Monitoring Committee (DSMC) will be the monitoring entity for this study. The DSMC will audit study-related activities to determine whether the study has been conducted in accordance with the protocol, local standard operating procedures, FDA regulations, and Good Clinical Practice (GCP). This may include review of the following types of documents participating in the study: regulatory binders, case report forms, eligibility checklists, and source documents. In addition, the DSMC will regularly review serious adverse events and protocol deviations associated with the research to ensure the protection of human subjects. Results of the DSMC audit will be communicated to the IRB and the appropriate regulatory authorities at the time of continuing review, or in an expedited fashion, as needed.

### 11.4 Data Management Plan

The Protocol Director, or designee, will prepare and maintain adequate and accurate subject case histories with observations and data pertinent to the study. Study specific Case Report Forms (CRFs) will document treatment outcomes for data analysis. Case report forms will be created in the Stanford Research Electronic Data Capture (REDCap) and will be maintained by the Protocol Director, co-Protocol Director, and clinical research coordinator team. All subjects will be registered in the OnCore database, allowing the Stanford SRC to judge the aggregate accrual and stopping rules for the study.

### 12. STATISTICAL CONSIDERATIONS

### 12.1 Statistical Design and Sample Size Determination

Statistical analyses of this non-randomized, phase 1B study will be primarily descriptive in nature. Formal statistical methods will not be used to determine the number of subjects per cohort/dose level in this phase 1B study. Summary statistics for discrete variables will be provided as frequencies and for continuous variables as the mean, standard deviation, median, and ranges.

Cohort 1 will utilize the combination of tamoxifen and infigratinib at 3 infigratinib dose levels (125 mg; 100 mg; and 75 mg). This combination may play a role in the future development of infigratinib for hormone receptor-positive breast cancer, necessitating the establishment of their safety. For example, tamoxifen and infigratinib might be used in the early-stage, (neo)adjuvant setting as well as the late-stage, metastatic setting. Therefore, the design is based on patient resources and current drug development.

# 12.2 Interim analyses

There will be no additional statistical stopping rules other than the 3+3 design rule for Cohort 1 as described in Section 2.5, and there will be no planned interim analysis.

## 12.3 Descriptive Statistics and Exploratory Data Analysis

The exploratory elements described in Section 1.3 will be included in the descriptive statistics and exploratory data analyses.

# 12.4 Primary Safety Analysis

Cohort 1 (infigratinib plus tamoxifen) will follow the 3+3 design evaluating 3 infigratinib doses levels, starting at 100 mg infigratinib 3 weeks on/1 week off) and moving to, if needed, 75 mg or 125 mg infigratinib 3 weeks on/1 week off. Given the nature of this cohort to be a safety run-in and the limited number of available subjects for this population, intra-subject dose-escalation will be allowed. The risk with intra-subject dose-escalation is that a dose may be declared overly toxic when the toxicities should be attributed to the number of cycles rather than the dose, but it is believed this is a conservative approach focused on subject safety.

Initially, 3 subjects will be treated at 100 mg for 2 cycles. If there are no DLTs observed in a subject at 100 mg after 2 cycles, the subject will escalate to 125 mg for 2 additional cycles. If 1 DLT is observed at 100 mg, an additional 3 subjects will be treated at 100 mg. If 2 or more DLTs are observed at 100 mg, an additional 3 subjects will be treated at 75 mg. If 1 DLT is observed at 75 mg, an additional 3 subjects will be treated at 75 mg. If no DLTs are observed in the first 3 subjects at 100 mg, but 1 DLT is observed at 125 mg, an additional 3 subjects will be treated at 125 mg, an additional 3 subjects will be treated at 125 mg. If 2 or more DLTs are observed at 125 mg, Cohort 1 will close. If a dose achieves no DLTs in 3 subjects after 2 cycles or 1 DLT in 6 subjects after 2 cycles, that dose will be declared safe for use in the main phase 2 trial.

If a subject withdraws prior to the completion of the first 2 cycles of therapy without having experienced a DLT, an additional subject will be enrolled at that dose level.

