
# 2.5 Study Design

- The primary purpose for this study is treatment. The protocol is designed to evaluate one or more interventions for treating a disease, syndrome, or condition.
- The interventional model is Sequential.
- The number of intervention arms is up to 3.
- The study will be not be masked (not blinded).
- The study will be not be randomized.

This is a phase 1b study evaluating the safety and tolerability of infigratinib. Cohort 1 will utilize the combination of tamoxifen and infigratinib. We anticipate that this combination may play a role in the future development of infigratinib for hormone receptor-positive breast cancer, necessitating the establishment of their safety. For example, tamoxifen and infigratinib might be used in the early-stage, (neo)adjuvant setting as well as the late-stage, metastatic setting.

In Cohort 1, up to 3 dose levels of infigratinib may be evaluated (125 mg; 100 mg; and 75 mg) in combination with tamoxifen. This pilot study is a necessary step for the future development of infigratinib in combination with tamoxifen and will serve as a safety run-in evaluation for a follow-up study. For this cohort, a 3 + 3 design will be employed starting at 100 mg, and allowing subjects who start at 100 mg to escalate to 125 mg (see Section 12.4).

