#### 10. MEASUREMENTS

### 10.1 Primary endpoint:

The primary endpoint is the incidence of dose-limiting toxicities (DLTs) in the first 2 cycles of therapy at a specific dose. In Cohort 1, in a subset of subjects who start at infigratinib 100 mg and complete 2 cycles with no DLTs and who remain on study for Cycles 3 and 4, the dose of infigratinib will be increased to 125 mg starting with Cycle 3 and the number of DLTs in Cycles 3 and 4 will be counted toward the primary endpoint (for the 125 mg dose), in addition to the number of DLTs in Cycles 1 and 2 (for the 100 mg dose). For all other subjects, the primary endpoint will be the number of DLTs in Cycles 1 and 2.

DLTs will be graded using NCI CTCAE (Common Terminology Criteria for Adverse Events), v5.0. DLTs will be defined as an adverse event (AE) or abnormal laboratory value at least possibly related to therapy with infigratinib including those AEs and abnormal laboratory values that result in a failure to meet the criteria for re-treatment. The criteria for defining a DLT, which are pre-specified based on the pre-clinical toxicity of infigratinib, are listed in Table 7.

Individual subjects who had a DLT may be retreated, after recovery, at the next lowest dose level.

Investigators will notify QED Therapeutics within 7 days of any DLTs observed.

**Table 7.** Criteria for defining dose-limiting toxicities

TOXICITY	DLT CRITERION
Skipped/ delayed dose	The inability to administer infigratinib on ≥ 75% of scheduled treatment days during cycle 1 at that dose (ie, ≥ 16 days of the 21 days of planned treatment) due to unresolved adverse event of any grade and considered at least possibly, probably, or definitely related to the study drug.
	Delay in 2 nd cycle administration at that dose due to failure of recovery from a possibly, probably, or definitely related adverse event to Grade ≤ 1 or baseline by Day 43 (Day 28 of Cycle 1 + 15 days), except for alopecia.
Blood/ bone marrow	Neutropenia     • Febrile, CTCAE Grade ≥ 3.     • CTCAE Grade ≥ 3 for > 7 consecutive days
	Thrombocytopenia
	Anemia CTCAE Grade 4
Renal/ genitourinary	Creatinine:  • CTCAE Grade 1 for > 7 consecutive days and serum inorganic phosphorus  > 5.5 mg/dL and/or serum total calcium x serum inorganic phosphorus  > 55 mg²/dL² and despite phosphorus lowering therapy for ≥ 14 days
	
 
CTCAE Grade 2 for > 7 consecutive days
 
CTCAE Grade ≥ 3
 

**Table 7.** Criteria for defining dose-limiting toxicities

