### 12.9 Criteria for future studies

If an MTD for infigratinib in combination with tamoxifen is identified with an acceptable number of DLTs (see Section 12.4), the combination will be deemed acceptable for future studies in this biomarker-selected population of advanced breast cancer. Should this combination prove safe, the study team is planning additional studies to assess efficacy in multiple populations of breast cancer subjects whose tumors harbor FGFR pathway alterations.

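### Escalation from 100 to 125 mg depends only on each subject's own result, so as written 125 mg can be given, and declared safe, after 100 mg has failed

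*Combined protocol and SAP*

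**What the plan says.** Section 12.4 starts three subjects at 100 mg and gives the escalation rule at subject level: "If there are no DLTs observed in a subject at 100 mg after 2 cycles, the subject will escalate to 125 mg". Section 10.1 describes the same step, from 100 to 125 mg, for subjects who "complete 2 cycles with no DLTs and who remain on study for Cycles 3 and 4, the dose of infigratinib will be increased", and counts their Cycle 3 and 4 DLTs toward the primary endpoint at 125 mg.

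The rules at dose level, also in 12.4, are:

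- One DLT at 100 mg adds three subjects at 100 mg.
- For failure of 100 mg: "If 2 or more DLTs are observed at 100 mg, an additional 3 subjects will be treated at 75 mg".
- For expansion at 125 mg: "If no DLTs are observed in the first 3 subjects at 100 mg, but 1 DLT is observed at 125 mg", three more subjects are treated at 125 mg.
- Two or more DLTs at 125 mg close Cohort 1.
- For declaring a dose safe for the phase 2 trial: "If a dose achieves no DLTs in 3 subjects after 2 cycles or 1 DLT in 6 subjects after 2 cycles".

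Other sections add no condition. Section 12.2 says "There will be no additional statistical stopping rules other than the 3+3 design rule for Cohort 1 as described in Section 2.5". Section 2.5 names a 3+3 design and refers back to 12.4 for the escalation. Section 12.9 sends the reader to 12.4 for the acceptable number of DLTs.

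**The concern.** The trigger for going up is the subject's own two DLT-free cycles. The rule for failure at 100 mg says where new subjects go. It does not say what happens to DLT-free subjects still at 100 mg or already at 125 mg. The one clause that links 125 mg to the 100 mg cohort governs only expansion at 125 mg.

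Two things are at stake. First, a subject can be sent above a dose that the same section has just rejected. Second, 125 mg can meet the safe-dose rule on its own data and be carried into phase 2 although 100 mg failed. The second bears directly on the primary objective in Section 1.1, which is the maximum dose up to 125 mg.

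Section 12.4 does discuss a risk of escalating within subjects, but it is the opposite one: that a dose is called too toxic because of cumulative exposure. Escalation within subjects is reasoned there and is not questioned here.

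**Working it through.** Notation: x/n means x subjects with a DLT among n evaluable.

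**1. The plan's own figure.** Counting new subjects along every path of 12.4 reproduces the synopsis range of 3 to 12. The minimum is 0/3 at 100 mg, with the same three escalating. The maximum is 1/3, then expansion to 6 at 100 mg, failure, then 3 + 3 at 75 mg: 6 + 6 = 12.

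**2. What the text does after 100 mg fails.**

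| Result at 100 mg | New subjects | DLT-free subjects due to escalate | Can 125 mg meet the safe-dose rule? |
|---|---|---|---|
| 2/3 | 75 mg | 1 | No, fewer than 3 |
| 3/3 | 75 mg | 0 | No |
| 2/6 | 75 mg | 4 | Yes, if at least 3 complete and none has a DLT |
| 3/6 | 75 mg | 3 | Yes, if all 3 complete without a DLT |
| 4/6 | 75 mg | 2 | No, fewer than 3 |

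This step needs no assumed rate.

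**3. Size for a truly toxic pair.** DLT rates with tamoxifen are not in the documents. Assume p = 0.30 at 100 mg and q = 0.40 at 125 mg.

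- P(1/3) = 3 × 0.3 × 0.7² = 0.441; P(2/3) = 3 × 0.3² × 0.7 = 0.189.
- P(2/6) = 0.441 × 0.441 = 0.1945; P(3/6) = 0.441 × 0.189 = 0.0833.
- Independent tolerance, all completing Cycle 4: 0.1945 × 0.6⁴ + 0.0833 × 0.6³ = 0.0252 + 0.0180 = **4.3%**.
- Fully nested tolerance (whoever tolerates 125 mg also tolerates 100 mg): the conditional rate is (0.4 − 0.3)/0.7 = 0.143, so 0.1945 × 0.857⁴ + 0.0833 × 0.857³ = 0.1050 + 0.0525 = **15.7%**.

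**4. With drop-out.** Let c be the share who complete Cycle 4 and s the chance of no DLT at 125 mg (0.6 or 0.857). The chance that at least three complete and none has a DLT is (cs)⁴ + 4(cs)³(1 − c) for four escalators and (cs)³ for three.

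- c = 0.63 comes from the 5.5-month median PFS that Section 2.3.1 quotes for another regimen, assumed exponential: exp(−ln 2 × 16/23.9 weeks) = 0.63.
- Independent: 0.1945 × 0.1004 + 0.0833 × 0.0540 = **2.4%**. Nested: 0.1945 × 0.3181 + 0.0833 × 0.1575 = **7.5%**.
- 63% is a low value, because 12.4 replaces subjects who leave in the first two cycles without a DLT. From the end of Cycle 2 the same median gives exp(−ln 2 × 8/23.9) = 0.79. With c = 0.8 the results are 3.7% and 12.0%.

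**5. The 2/3 case.** At p = 0.30 its probability is 18.9%. This is an upper figure for escalation after a known failure, since some remaining subjects will have escalated before the second DLT is seen.

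**6. Single-agent rates, for comparison only.** Section 2.2.9 gives 1/6 at 100 mg and 1/8 at 125 mg. With P(2/6) = 0.1206 and P(3/6) = 0.0241, the declaration after failure has probability 0.1206 × (7/8)⁴ + 0.0241 × (7/8)³ = 8.7%. Here 125 mg is assumed less toxic than 100 mg, so most of this is 100 mg failing by chance.

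**7. Lesser gap.** After 1/6, 100 mg is cleared and five DLT-free subjects escalate. One DLT among them meets no enrolment rule, because expansion at 125 mg is written only for 0/3 at 100 mg. At p = 0.30, P(1/6) = 0.441 × 0.343 = 0.151. The probability of this event, if all five stay, is 0.151 × 5 × 0.4 × 0.6⁴ = 3.9% (independent) or 0.151 × 5 × 0.143 × 0.857⁴ = 5.8% (nested).

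**The case against.** The strongest reply is that 12.4 opens by placing the cohort under a 3+3 design, moving to 75 or 125 mg if needed, and that 12.2 makes the 3+3 the stopping rule. By convention a 3+3 does not go above a failed dose. Section 2.5 is permissive in tone, "allowing subjects who start at 100 mg to escalate to 125 mg (see Section 12.4"), and de-escalation of new subjects points the right way. A reader might infer from the gap that the plan chose to dose above a failed level. The documents do not support that; they show a subject-level sentence without a written gate. But the label does not settle the matter, because an explicit instruction that the subject will escalate stands beside it, and escalating within subjects already departs from the convention.

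Individual risk is also bounded, and this stands. Escalated subjects have had two DLT-free cycles at 100 mg, 125 mg is the single-agent MTD, Section 6 sets holds and reductions, and two DLTs at 125 mg close the cohort. After 2/3 only one subject is affected. None of this prevents the wrong declaration after 2/6 or 3/6.

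A reader might take the 8.7% as the chance of harm. It is not, for the reason given in step 6.

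A reader might also infer from the lesser gap that the trial would end without a dose. It would not: 100 mg is already cleared, the 1-in-6 threshold for 125 mg exists, and if all five stay only a sixth subject is lacking. The expansion sentence also states its action twice, which suggests a drafting slip, so its exact wording should not carry much weight.

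**Conclusion.** The concern holds. As written, 12.4 and 10.1 allow 125 mg to be given after 100 mg has failed, and allow it to be declared safe after 2/6 or 3/6 at 100 mg. That conclusion rests on the text alone.

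The size rests on assumptions. For true rates of 30% and 40%, the wrong declaration has probability 4.3% to 15.7% with everyone completing Cycle 4, and 2.4% to 7.5% if 63% do. The upper end needs fully nested tolerance and no drop-out.

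The missing expansion rule after 1/6 is a clarification. A usable dose exists, but whether 125 mg is the maximum dose could not be settled by a rule written in advance. That matters because 12.9 makes further studies conditional on this result: "If an MTD for infigratinib in combination with tamoxifen is identified with an acceptable number of DLTs".

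This should be corrected before the rule is applied, because it concerns subject safety and the primary objective and costs little to repair.

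**What to change.** Amend 12.4 and match it in 10.1:

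1. Once 2 or more subjects have had a DLT at 100 mg, no further subject escalates to 125 mg. A subject already at 125 mg without a DLT is reviewed individually for reduction or continuation, and those Cycle 3 and 4 data cannot support a safe declaration.
2. 125 mg can be declared safe only if 100 mg has been cleared (0/3 or 1/6). This is needed as well as rule 1, because some subjects will have escalated before the second DLT at 100 mg is seen.
3. As a clarification, once 100 mg is cleared by either route, one DLT at 125 mg leads to expansion to 6 evaluable subjects at 125 mg.

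Rules 1 and 2 bring the probability of declaring 125 mg safe after 100 mg has failed to zero. The cost is a few sentences. The maximum stays at 12 evaluable: up to 6 at 100 mg plus up to 6 new at 75 or 125 mg. The downside is slightly less 125 mg data when 100 mg fails. Escalation is unchanged unless 2 or more subjects have a DLT at 100 mg. Whether a subject tolerating 125 mg should come down is a clinical trade-off, so rule 1 leaves it to individual review.

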# **PROTOCOL SYNOPSIS**

TREATMENT SUMMARY	Infigratinib is an oral selective FGFR1-3 inhibitor that has been tested in phase 1 and 2 clinical trials as a single agent. This phase 1B study will assess the safety and tolerability of infigratinib in combination with the FDA-approved dose and schedule of tamoxifen (Cohort 1). In Cohort 1, up to 3 dose levels of infigratinib will be evaluated: 125 mg; 100 mg; and 75 mg, starting with the middle dose level (100 mg). Infigratinib will be administered orally daily, 3 weeks on, 1 week off. Subjects will also be given tamoxifen 20 mg orally continuously. If toxicity presents, individual subjects may dose-reduce by 25 mg infigratinib per reduction, to a lower limit of 75 mg infigratinib (See Sections 2.5 and 6).
	Treatment with study drug will continue for 18 months or confirmed disease progression, unacceptable toxicity deemed probably-related to study drug, whichever occurs first, or other reasons outlined in Section 4.3 .
SAMPLE SIZE	Up to 12 subjects evaluable (minimum 3), not including subject replacement.

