# 4.1 General Concomitant Medication and Supportive Care Guidelines

#### 4.1.1 Concomitant Medication

Administration of other anticancer therapies within 2 weeks of enrollment, except ongoing administration of a bisphosphonate drug or denosumab as treatment for bone metastasis or ongoing administration of a luteinizing hormone-releasing hormone agonist (such as goserelin acetate or leuprolide acetate) or other endocrine therapy, is prohibited.

Palliative radiotherapy on study is permitted for the treatment of painful bony lesions providing the lesions were known at the time of study entry and the investigator clearly indicates that the need for palliative radiotherapy is not indicative of disease progression. In view of the current lack of data about the interaction of infigratinib with radiotherapy, infigratinib treatment should be interrupted during palliative radiotherapy, resuming infigratinib treatment after recovery to ≤ Grade 1 radiotherapy-related toxicity.

Details for specific medications prohibited while on study are provided in Appendix A. The rationale for the restricted medications is provided below.

Strong inhibitors of CYP3A4 such as the ones listed in Appendix A are prohibited because infigratinib is a likely substrate of this isoenzyme.

Strong inducers of CYP3A4 are prohibited because their usage may decrease the exposure of infigratinib. Therefore, agents such as those listed in Appendix A are prohibited. Please note that the list may not be exhaustive.

Subjects must also avoid the consumption of grapefruits; grapefruit juice; grapefruit hybrids; pomegranates; star fruits; pomelos; Seville oranges; or juice within 7 days prior to the first dose of infigratinib and throughout the treatment period due to a potential CYP3A4 interaction with study drug.

Medications that increase the serum levels of phosphorus and/or calcium are prohibited.

Preliminary clinical data have shown that infigratinib has no effect on cardiac conduction or ECG intervals (See current version of the infigratinib Investigator's Brochure). However, medications that are known to prolong the QT/QTc interval or induce TdP (risk of TdP/QT prolongation) are prohibited. List of these medications is given in Appendix A. Please note that the list might not be comprehensive.

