Medications that are allowed but should be administered with caution are provided in Appendix B. The rationale for these medications is provided below.

Infigratinib is characterized by pH-dependent solubility, and therefore, medicinal products that alter the pH of the upper GI tract may alter the solubility of infigratinib, and limit bioavailability. These agents include, but are not limited to, proton pump inhibitors (eg, omeprazole), H2-antagonists (eg, ranitidine) and antacids. If possible, proton pump inhibitors should be avoided due to their long PD effect and replaced with  $H_2$ -antagonists or antacids. Study drug should be taken  $\geq 2$  hours before or 10 hours after dosing with a gastric protection agent.

Infigratinib is a substrate of CYP3A4. Therefore, moderate inhibitors and inducers should be used with caution if an alternative is not available. If anticoagulation is required, heparin and/or low-molecular-weight heparins or direct thrombin inhibitors and/or Factor Xa inhibitors that are not metabolized by CYP3A4 (eg, dabigatran, edoxaban) are preferred. If unavoidable, anticoagulants that are CYP3A4 substrates and have a narrow therapeutic index [eg, warfarin sodium or any other coumadin-derivative anticoagulants or certain direct thrombin inhibitors (eg, argatroban or Factor Xa inhibitors, eg, rivaroxaban)] should be used with caution.

Infigratinib was shown in vitro to inhibit the drug transporter breast cancer resistance protein (BCRP), with an IC50 of 210 nM. While the clinical relevance of this inhibition is unknown, drugs transported by BCRP should be used with caution.

Anti-emetics are recommended as clinically appropriate at the first sign of nausea and vomiting or as prophylaxis to prevent emesis, along with supportive care according to clinical practice guidelines.

It is recommended to avoid using drugs that are known to cause QT prolongation. Note that some anti-emetics have a known risk for Torsade de Pointes, and therefore need to be used with caution. See Appendix B for list of drugs that need to be used with caution. Aprepitant (brand name: Emend) is both a sensitive substrate and a moderate CYP3A4 inhibitor and should be used with caution if an alternative is not available.

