# 12.7 Analysis Population

All subjects who received at least one dose of the study drug (infigratinib) will be analyzed for the safety and efficacy outcomes outlined in sections 12.4; 12.5; and 12.6.

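### A subject who misses much of the infigratinib in the DLT window for a reason unrelated to the drug still counts as DLT-free, because the plan never defines DLT-evaluable by doses received

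*Combined protocol and SAP*

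**What the plan says.** - **Decision rule (Section 12.4).** "If a dose achieves no DLTs in 3 subjects after 2 cycles or 1 DLT in 6 subjects after 2 cycles", the dose is declared safe for the later phase 2 trial.
- **Replacement (Section 12.4).** "If a subject withdraws prior to the completion of the first 2 cycles of therapy without having experienced a DLT, an additional subject" is enrolled at that dose level. No other event triggers replacement.
- **Missed doses as a DLT (Section 10.1, Table 7).** Failure to give infigratinib on at least 75% of scheduled days (16 of 21) is a DLT, but only in Cycle 1 and only when "due to unresolved adverse event of any grade and considered at least possibly, probably, or definitely related to the study drug".
- **Permitted interruption (Section 4.1.1).** Palliative radiotherapy to painful bone lesions known at entry is allowed, and "infigratinib treatment should be interrupted during palliative radiotherapy, resuming infigratinib treatment after recovery to ≤ Grade 1 radiotherapy-related toxicity". Nothing excludes the DLT window.
- **Skipped doses (Section 5.1.2).** Missed doses are not made up, and there is no re-dosing on the same day after vomiting.
- **Escalation (Sections 10.1 and 12.4).** A subject without a DLT after 2 cycles at 100 mg moves to 125 mg, and Cycles 3 and 4 then count toward the 125 mg decision.
- **Sample size (Synopsis).** "Up to 12 subjects evaluable (minimum 3), not including subject replacement". The documents do not define evaluable.
- **Analysis population (Section 12.7).** "All subjects who received at least one dose of the study drug (infigratinib) will be analyzed for the safety and efficacy outcomes" of Sections 12.4 to 12.6.

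**The concern.** A 3+3 decision treats each DLT-free subject as evidence that the dose was taken and tolerated. Under the rules as written, a subject can finish two cycles without a DLT partly because a good share of the drug was not given. If the reason is unrelated to the drug, no rule removes that subject from the count.

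Fewer doses can be expected to lower the chance of a DLT, or at least not to raise it. The error from missed doses therefore runs toward declaring a dose safe. Each decision rests on 3 to 6 subjects, so one such subject carries real weight. The same gap returns in Cycles 3 and 4 at 125 mg. A subject can also reach 125 mg without any check that the 100 mg course was largely received. Bone-only disease is eligible (Section 3.1), so a hold for bone radiotherapy is a plausible route.

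**Working it through.** **The plan's own figures.** Up to 6 subjects at 100 mg plus up to 6 new subjects at 75 mg gives 12. The minimum is 3, when the same three subjects show no DLT at 100 mg and again at 125 mg. In Table 7, 0.75 × 21 = 15.75, which rounds up to the stated 16 days. Both figures reproduce.

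**How many missed days matter.** Six lost dosing days leave 15 of 21 (71%), below the Table 7 threshold. A one-week hold that falls entirely on dosing days (assumed length) leaves 14 of 21 (67%) in that cycle and 35 of 42 (83%) over the two-cycle window. A hold in Days 22 to 28 costs no doses.

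**What the rules do with that subject.**
1. The Table 7 missed-dose row does not apply, because the cause is not a drug-related adverse event. In Cycle 2 the row does not apply whatever the cause.
2. The Section 12.4 replacement rule does not apply, because the subject has not withdrawn.
3. The subject counts as DLT-free at that dose and, if at 100 mg, escalates.

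**Effect on the decision.** Let p be the DLT risk of a fully exposed subject and r that of one under-exposed subject among the first three.

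- No DLT in the first three: A = (1−r)(1−p)²
- Exactly one DLT in the first three: B = r(1−p)² + (1−r)·2p(1−p)
- P(declared safe) = A + B(1−p)³

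With everyone fully exposed, r = p. At p = 0.40 this gives 0.216 + 0.432 × 0.216 = 0.309.

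One under-exposed subject at p = 0.40:
- Risk cut in proportion to doses (r = 0.40 × 35/42 = 0.333): 0.240 + 0.440 × 0.216 = 0.335
- Risk halved (r = 0.20): 0.288 + 0.456 × 0.216 = 0.386
- Risk removed (r = 0): 0.360 + 0.480 × 0.216 = 0.464

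| True DLT rate p | All fully exposed | r = 5/6 of p | r = half of p | r = 0 |
|---|---|---|---|---|
| 1/6 (single agent, 100 mg: 1 of 6, Section 2.2.9) | 0.780 | 0.792 | 0.817 | 0.855 |
| 1/3 (seen only at 150 mg: 2 of 6) | 0.428 | 0.453 | 0.502 | 0.576 |
| 0.40 (assumed) | 0.309 | 0.335 | 0.386 | 0.464 |

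**Allowing for frequency.** The rows above assume that one such subject occurs. Suppose instead that each subject has a 10% chance of being under-exposed (assumed). At p = 0.40 the average risk is 0.40 × 0.95 = 0.38 if risk is halved and 0.40 × 0.90 = 0.36 if it is removed. P(declared safe) is then 0.343 or 0.378, against 0.309.

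**The case against.** Much can be said for the plan as written, and several stronger readings fail.

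- **That the loss of exposure would go unseen.** A reader might infer this because no routine drug level is scheduled. The documents do not support it. Serum phosphorus is scheduled at screening, on Days 1, 4 and 15 of Cycle 1 and on Days 1 and 15 of Cycle 2 (Section 9), and Section 7.1.1 treats its rise as a reliable marker of pathway inhibition. Drug accountability is captured at each visit (Section 5.4) and co-medication is recorded. What is missing is a rule for using that information in the DLT count.
- **That permitted co-medication biases the count toward safety.** Section 4.1.1 says "If possible, proton pump inhibitors should be avoided due to their long PD effect", lets moderate CYP3A4 inducers be used with caution, and warns that drugs altering gastric pH may limit bioavailability. But it applies dose spacing to gastric agents generally, and it states reduced exposure only for strong inducers, which are prohibited. Moderate CYP3A4 inhibitors are allowed on the same terms and could act the other way. The net direction is not established, and no document supports a cut-off for excluding such subjects.
- **That a single dose makes a subject count as evidence of safety.** Section 12.7 does name Section 12.4, but the decision rule itself refers to subjects after 2 cycles and early withdrawals are replaced. The gap concerns subjects who stay on study.
- **The radiotherapy route is narrow.** It is limited to known painful bone lesions whose treatment does not signal progression, and earlier radiotherapy must end at least 2 weeks before the study drugs start. This stands, and it limits how often the problem would arise.
- **The size depends on assumptions.** This also stands. True DLT rates of 1/3 to 0.40 are not documented for any dose in this trial, and the loss of risk per missed dose is unknown.

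None of these points supplies a definition of evaluable or changes how a subject with a hold unrelated to the drug is counted.

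**Conclusion.** The gap is real and narrow. Followed literally, Sections 10.1 and 12.4 count a subject who missed a material share of doses for reasons unrelated to the drug as DLT-free, in Cycles 1 and 2 and again in Cycles 3 and 4 at 125 mg.

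One such subject among the first three adds about 3 to 15 percentage points to the chance of declaring safe a dose with a true DLT rate of 40%, and about 1 to 8 points at a rate of 1/6. This assumes that DLT risk falls at least in proportion to the doses missed, up to complete removal, and that such a subject occurs. The documents give neither the frequency of holds nor the size of the effect, so they do not show that a dose is likely to be wrongly declared safe. This is a cheap improvement, not a flaw that undermines the design.

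**What to change.** 1. In Sections 12.4 and 12.7, define a DLT-evaluable set for the 3+3 decisions and give the word evaluable in the Synopsis the same meaning. A subject is evaluable at a dose if they had a DLT at that dose, or if they completed the two-cycle window at that dose with at least 75% of planned infigratinib doses in each cycle (16 of 21 days, the Table 7 figure).
2. Replace DLT-free subjects below that threshold for reasons other than a drug-related adverse event, through the existing Section 12.4 mechanism. Those below it because of a drug-related adverse event stay in the denominator and are not replaced, so tolerability information is kept. DLTs always count.
3. Apply the same rule to Cycles 3 and 4 at 125 mg. Reconcile Sections 10.1 and 12.4 on whether a subject not evaluable at 100 mg enters the 125 mg evaluation; that choice is the sponsor's.
4. Beside each DLT decision, list the use of exposure-lowering and exposure-raising co-medication in the window, from data already collected. Do not make it an exclusion criterion.
5. Keep the at-least-one-dose population for adverse event and efficacy summaries.

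The cost is protocol wording and an occasional replacement subject, each followed for two cycles (56 days). The maximum of 12 already leaves replacements out. If 10% to 20% of subjects needed replacing (assumed), enrolment on the longest path would be 12/0.9 = 13.3 to 12/0.8 = 15, that is 14 to 15 subjects. Permitted treatment does not change.
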